Participants in Cohort A who are assigned to the control group will receive education regarding treatment consideration from their healthcare provider/team as per standard practice (usual care).

Participants in Cohort A who are assigned to the intervention group will receive education regarding treatment consideration from their healthcare provider/team as per standard practice. Additionally, they will be provided access to the decisional aid and will be provided with a unique access ID and password for purposes of this study. Participants will receive follow-up monthly via telephone call and/or e-mail to verify ability to access and navigate through website.

Visit 2

Participants will be scheduled for the second research visit to coincide with the completion of education presented by the healthcare provider/team. Participants will be asked to complete the study surveys within 2 weeks following the office/clinic visit via paper version or on-line. Self-report information regarding themselves or the patient they care for will be updated relating to sickle cell disease management and complications since Consent/Visit 1. Participants will receive follow-up monthly via telephone call and/or e-mail to verify ability to access and navigate through website.

Visit 3

Participants will be scheduled for the final research visit within 4 months of the completion of education and discussion with their healthcare provider/team. Participants will be asked to complete the study surveys as well as either via paper versions or online within 2 weeks following this office/clinic visit:

- Decision Regret Scale (*5 multiple choice*)
- Additionally, a qualitative interview will be conducted with the participants within 4 weeks of visit 3 to evaluate the extent to which the method of educational tools (standard practice or decision aid) helped the participant to recognize that a decision needs to be made regarding treatment of sickle cell disease, to understand the values that affect the decision, and understand if and how these values were addressed with the health care provider. Interviews will take approximately 30-45 minutes for completion. Interviews will

be audio recorded and transcribed verbatim for later analysis. Interviews will be conducted in a private setting, away from family members and clinical staff.

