Self-report information regarding themselves or the patient they care for will be updated relating to sickle cell disease management and complications since Visit 2.

Cross-Over

After completion of final study visits/surveys and data collection, participants in the control group for Cohort A will be offered opportunity to visit the Decision Aid website. Participants will be given 4 weeks to review this site, at which time they will be asked to complete a series of questionnaires via paper version or electronically:

- Acceptability of education (*8 multiple choice, 2 short answer*)
- Decision Self-Efficacy Scale (*11 multiple choice*)
- Decisional Conflict Scale (*16 multiple choice*)
- Stage of Decision Making (*10 multiple choice*)
- Values survey (*14 multiple choice, 6 fill in the blank*)
- Realistic Expectations (*multiple choice*)
- Preparation for Decision Making Scale (*10 multiple choice*)
- Knowledge Survey (*25 multiple choice*)
- Choice Predisposition and Decision (*1 multiple choice and 4 fill in the blank*)
- Decision Regret Scale (*5 multiple choice*)

Participants => 18 years of age will complete:

- Emotional distress Anxiety – short form 6a – participant version
- Depression – short form 6a – participant version
- Fatigue – short form 6a – participant version
- Pain interference – short form 6a – participant version
- Physical Function – short form 8b – participant version
- Ability to participate in social roles and activities – short form 6a – participant version

Participants of children <18 years of age will complete:

- Fatigue – short form 10 – parent proxy
- Mobility – short form 8 – parent proxy
- Peer relations – short form 7 – parent proxy
- Anxiety – short form 8b – parent proxy
- Depressive symptoms – short form 6b – parent proxy

A qualitative interview will be conducted within 4 weeks of completion of the questionnaires to understand participant-perceived comparison of supportive care in decision making versus use of the Decision Aid tool. Participants will be asked to discuss the affect, if any, on their treatment decision prior to use of the Decision Aid tool. Participants will receive follow-up monthly via telephone call and/or e-mail to verify ability to access and navigate through website after receiving access to the decision aid.

Cohort B

Consenting/Visit 1

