Qualitative analysis will be performed using qualitative descriptive methods which is influenced and a similar to interpretive descriptive analysis. Qualitative descriptive^{45,46} analysis requires less interpretation than other types of qualitative analysis, such as phenomenological or interpretive description. Qualitative description lends itself to a more straightforward analysis that, by the nature of its methods, lends itself to this study. Analysis of these data will rely on components of the Ottawa Decision Support Framework for development of a codebook. This framework provides operational definitions of needs in the decision making process, such as decisional conflict (uncertainty), knowledge and expectations, personal values, and support/resources available. Additionally, data will be quantized or translated to numerical data for improved understanding of results⁴⁷. This method of analysis allows for quantification of themes, patterns, and idiosyncrasies unique to qualitative research that may otherwise be discarded as outliers in quantitative analysis⁴⁷.

We propose a randomized controlled trial of decision aid vs. usual care to determine its impact on previously defined endpoints measuring decisional process and decisional quality.

Avoidance of bias

Selection biases occur when the groups to be compared are different. We anticipate that randomization will avoid selection bias as well as volunteer or referral bias. A *drop out analysis will be carried out to determine the contribution of attrition bias*. Measurement biases involve systematic error that can occur in collecting relevant data and include, insensitive measure bias, expectation bias, recall or memory bias, attention bias, and verification or work-up bias. Systematic validation of the decision aid will avoid *insensitive measure bias* which occurs when instruments used are not sensitive enough to detect what might be important differences in the variable of interest. The risk of *Expectation bias*, when observers may err in measuring data toward the expected outcome will be avoided by masking or blinding the reviewer of the survey about the arm to which the patient was randomized. Recall or memory bias which can occur if outcomes being measured require that subjects recall past events will be avoided by administering surveys within days of the interaction with their health care provider.

Human Subjects

Protected Health Information

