Research staff directly involved in the study will have access to data collected during this study. Paper documents will be filed in a locked filing cabinet in a secure office setting. Electronic data will be maintained on a secure Hematology/Oncology share-drive with limited access behind a secure firewall at Emory University. Participant data will be identified with a unique number. The key connecting the participant to the ID number will be maintained separately from the study data and will be destroyed upon completion of the study, to include dissemination of findings. The ID key will be accessible only to members of the research team. All audio recordings will be identified on the recording with the unique participant identification number. All transcripts will be identified using the participant identification number and names of parents and health care providers will be indicated with "XXX" in the transcription. Audio transcriptions will be destroyed after transcription is complete and verified, analyzed and findings are disseminated.

The data and safety monitoring team will include the Principal Investigator and the study coordinator. Meetings will occur every 3 months from time of enrollment of the first patient. DSMP reports will be generated for each meeting. Any information regarding increased risks, modifications necessary to ensure patient safety, and adverse events will be discussed and submitted to the IRB according to established guidelines. All study data reviewed and discussed during these meetings will be kept confidential. Any breach in confidentiality will be reported to the IRB and regulatory agencies. The investigator will continue to review all available information and study results regarding this patient population. The PI will report to the IRB within 24 hours any serious adverse event occurring that is associated with this research study. Unexpected adverse events of moderate severity in association with the research intervention will be reported to the IRB within 5 business days. Reporting of adverse events to sponsors and federal agencies will be the responsibility of the investigator.

Withdrawal from Study

The participant may withdraw from the study at any time by notifying the PI and/or the research team. All data collected up until the point of withdrawal will be included in data analysis. No further data will be collected.

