The participant may be withdrawn from the study if the participant does not participate in the educational process of usual care or if the participant assigned to intervention does not view the website prior to the next scheduled clinic appointment or does not show for the next appointment and does not reschedule that appointment within 4 weeks of the originally scheduled appointment.

Compensation

Study participants, (patients, parents/legal guardians) will be provided with a \$25 gift card for each completed set of survey questions.

Participants (patients, parents/legal guardians and caregivers) will be provided with a \$25 gift card for completion of each qualitative interview.

Healthcare providers and stakeholders will be given a sickle cell tie, bowtie or scarf for their participation in this study.

There will be no compensation provided for participation in the Hindi beta testing.

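### Intervention participants can be withdrawn for not viewing the website, a ground controls cannot meet, and no outcome follow-up or as-randomized analysis protects the comparison

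*Combined protocol and SAP*

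**What the plan says.** The second paragraph of Withdrawal from Study lists the grounds on which the team may, but need not, withdraw someone:

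- "if the participant does not participate in the educational process of usual care". This can apply in either arm, because the Cohort A section gives the intervention group the same education: "Participants in Cohort A who are assigned to the intervention group will receive education regarding treatment consideration" from their provider under standard practice, with the website added.
- "if the participant assigned to intervention does not view the website prior to the next scheduled clinic appointment". By its own words this applies to the intervention arm alone.
- "does not show for the next appointment and does not reschedule that appointment within 4 weeks" of the original date. The sentence can be read as covering both arms or only the intervention arm.

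The Cross-Over section says that, once final surveys and data collection are complete, "participants in the control group for Cohort A will be offered opportunity to visit the Decision Aid website". No control can meet the website ground while the comparison is running.

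On data after withdrawal, the first paragraph of the section says: "All data collected up until the point of withdrawal will be included in data analysis. No further data will be collected".

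On timing, Cohort A, Visit 2 says: "Participants will be scheduled for the second research visit to coincide with the completion of education presented by the healthcare provider/team". The surveys are due within two weeks after that visit. Visit 3 follows within four months of the education and discussion.

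On missing outcomes, Avoidance of bias says only that a "drop out analysis will be carried out to determine the contribution of attrition bias". No method is given. The document names no analysis population, no as-randomized analysis and no handling of missing data.

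**The concern.** Aim 2 is to estimate, in a randomized trial, how effective the decision aid is against usual care. Randomization protects that comparison only if both arms are followed and analysed as allocated. Here at least one withdrawal ground depends on behaviour after randomization that can be observed in one arm only.

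People who do not open the website may differ from those who do in engagement with their care, which is close to what the trial measures. If they are withdrawn and not followed, the retained intervention arm is a selected group set against a control arm that has not been selected in that way. The result then answers neither what happens when the aid is offered nor, validly, what happens when it is used, because the controls who would not have viewed it remain in the comparison. Outcomes that were never collected cannot be recovered at analysis.

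**Working it through.** **1. What a withdrawn non-viewer contributes.** Viewing is judged against the next scheduled clinic appointment. Someone withdrawn at or before Visit 2 has no post-education survey. Someone withdrawn later, after the Visit 2 surveys, keeps those data but loses Visit 3. A drop-out analysis can describe these gaps but cannot fill them.

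**2. The plan's own figure.** Inputs from Sample Size Calculations: 30% involvement under standard care, doubled to 60%; 90% power; 0.05 level (taken as two-sided). The pooled normal formula gives

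n = [1.960·√(2·0.45·0.55) + 1.282·√(0.30·0.70 + 0.60·0.40)]² / 0.30² ≈ 56 per group,

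against the plan's 55, so the figure reproduces to within one patient per group. Recruiting 60 per group allows for 5 of 60 = 8.3% attrition, the same in each arm.

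**3. Bias when there is no true effect.** Assumptions, not plan figures: 60 randomized per arm; true involvement 30% in both arms; a fraction f of the intervention arm withdrawn as non-viewers; a gap g between viewers' and non-viewers' involvement. Since 0.30 = (1 − f)·p + f·(p − g), the retained rate is p = 0.30 + f·g. The bias is f·g if no controls are lost, and (f/2)·g if controls are lost at half the rate with the same gap. Type I error is from exact enumeration of two binomials with a pooled two-sided z-test at 0.05. With no removals it is 5.2%.

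| Scenario | f = 10% | f = 20% | f = 30% |
|---|---|---|---|
| No control losses, g = 0 | 5.4% | 5.4% | 5.1% |
| No control losses, g = 10 points | 5.6% (bias +1) | 6.0% (+2) | 6.4% (+3) |
| No control losses, g = 20 points | 6.2% (+2) | 7.8% (+4) | 10.0% (+6) |
| Half-rate control losses, g = 0 | 5.2% | 4.8% | 5.5% |
| Half-rate control losses, g = 10 points | 5.3% (+0.5) | 4.9% (+1) | 5.9% (+1.5) |
| Half-rate control losses, g = 20 points | 5.4% (+1) | 5.2% (+2) | 6.8% (+3) |

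The g = 0 rows show that movements of a few tenths of a point are partly discreteness. If non-viewers are the more involved group, the bias changes sign. If the plan's whole attrition allowance in the intervention arm were non-viewers (55 against 60), type I error is 5.0% with a 10-point gap (bias 0.083 × 10 = +0.8 points) and 5.2% with a 20-point gap (+1.7 points).

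**4. Shift in the estimated effect.** Suppose viewers gain 30 points, non-viewers gain nothing, and f = 20%.

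- As randomized: 0.30 × 0.80 = 24 points.
- After removal with no control losses: 30 + 0.20·g, which is 28, 30, 32 and 34 points for g = −10, 0, 10 and 20.
- After removal with half-rate control losses: 30 + 0.10·g, which is 29, 30, 31 and 32 points.

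**5. Power when non-viewers are kept.** If non-viewers respond at the control rate, the intervention rate is 0.30 + 0.30(1 − f). Power from the same exact test:

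| Per arm | f = 0 | f = 10% | f = 20% | f = 30% |
|---|---|---|---|---|
| 60 | 92% | 86% | 77% | 66% |
| 55 | 89% | 82% | 72% | 62% |

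**The case against.** **The rule may seldom bite.** Withdrawal is discretionary, internet access is an entry criterion, and monthly contacts check that participants can reach the site. These may keep non-viewing low. They do not remove the ground, and no criteria say when it is to be used.

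**The stop on data collection may not apply.** That sentence directly follows the one on participants who choose to leave, and nothing says outright that it covers withdrawal by the team. This stands as an ambiguity. But it falls under the same heading, no other rule covers team-initiated withdrawal, and withdrawal from the study would ordinarily end the surveys.

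**The asymmetry may be misjudged.** Controls can be lost through the education ground and perhaps through missed appointments. If those losses are of a similar kind, the bias shrinks, as the half-rate rows show. If the missed-appointment clause covers only the intervention arm, there are two arm-specific grounds, not one. The sentence needs clarifying either way.

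**The trial may want the effect of use.** The research questions and the description of Cohort A do speak of use of the aid. That leaves the target effect less than fully settled, but dropping non-viewers from one arm does not validly estimate the effect of use either.

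**The type I error change is small near the plan's own attrition.** This stands. The 10.0% figure needs 30% removal, a 20-point gap and no control losses, none of which comes from the documents.

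**The illustrated outcome may not be collected.** The involvement scale named under Expected Outcomes is absent from the Cohort A survey lists. That is a separate defect. The selection problem applies to whichever outcome is compared.

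**Conclusion.** The concern holds. As written, the plan permits removal after randomization on at least one ground confined to the intervention arm, with no stated outcome follow-up and no as-randomized analysis. It should be fixed; confidence in its practical weight is medium.

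Its size and direction cannot be known from the documents, which give neither a viewing rate nor outcomes in non-viewers. The main consequence is the change in what is estimated: under the stated assumptions at 20% non-viewing, a 24-point effect of offering the aid would appear as roughly 28 to 34 points. Inflation of type I error is secondary. It is negligible when withdrawals are few, and material only when removal is common, confined to one arm, and viewers differ clearly from non-viewers. The conclusion also rests on reading the stop on data collection as covering team-initiated withdrawal.

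**What to change.** - Remove website non-viewing as a reason to end outcome collection. Keep sending the existing paper or online surveys to every randomized Cohort A participant in either arm unless that person withdraws consent, and say that this also holds after the team withdraws someone from the intervention or the education.
- Reword the withdrawal sentence so that the arm or arms covered by the missed-appointment clause are clear.
- State that the primary analysis includes all randomized Cohort A participants in their assigned arm.
- Record website use, and report any viewers-only or complier analysis as secondary.

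The cost is protocol wording, some extra survey follow-up and a $25 card per completed set. The change itself needs no added enrolment. Its downside is that dilution from non-use becomes visible: if non-viewers gain nothing, the stated 90% power is not kept at 60 per arm once 10% or more do not view. Restoring it by numbers would take about 69, 87 or 113 per arm at 10%, 20% or 30% non-viewing (pooled normal formula, same assumptions). That reflects the effect of offering the aid and is not a loss caused by the fix.
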